# 14.2 APPENDIX B: Psoriasis Area Severity Index at the Target Lesion Site

Score	Grade	Erythema	Scaling	Plaque Elevation
0	Clear	No evidence of erythema	No evidence of scaling	No evidence of plaques above normal skin level
1	Almost Clear	Pink discoloration, minimal erythema	Occasional fine scales hardly noticeable	Slight, just discernible elevation above normal skin level
2	Mild	Light red coloration	Slight but definite roughness, fine scale present, no cracking	Discernible elevation above normal skin level upon examination, but not pronounced
3	Moderate	Moderate redness, but not dark	Moderate roughness, somewhat coarse scaling	Definite plaque formation with rounded/sloped edges to plaque
4	Severe	Dark red coloration	Marked roughness, coarse/thick scaling, cracking may be evident	Marked elevation with hard, distinct edges to plaque
5	Very Severe	Very dark red coloration with induration present	Very thick scales covering extensive area, severe cracking/fissures may be evident	Very marked elevation, very hard and sharp edges to plaque

To be eligible for participation in the study a subject must have a minimum plaque elevation of at least moderate severity (score  $\geq$  3) at the target lesion site. The most severe lesion at Baseline should be identified as the target lesion.

A Multi-Center, Double-Blind, Randomized, Vehicle-Controlled, Parallel-Group Study Comparing Tazarotene Cream 0.05% to TAZORAC® (tazarotene) Cream 0.05% and Both Active Treatments to a Vehicle Control in the Treatment of Stable Plaque Psoriasis

#### **14.3 APPENDIX C: Application Site Reactions**

The following application site reactions will be evaluated at each visit based on the scale provided below:

Signs and Symptoms: Erythema Dryness Burning/Stinging Erosion Edema Pain Itching

Grading Scale:

Severity	Grade
Absent	0
Mild	1 (slight, barely perceptible)
Moderate	2 (distinct presence)
Severe	3 (marked, intense)

A Multi-Center, Double-Blind, Randomized, Vehicle-Controlled, Parallel-Group Study Comparing Tazarotene Cream 0.05% to TAZORAC® (tazarotene) Cream 0.05% and Both Active Treatments to a Vehicle Control in the Treatment of Stable Plaque Psoriasis

14.4 APPENDIX D: TAZORAC® (tazarotene) Product Insert

A Multi-Center, Double-Blind, Randomized, Vehicle-Controlled, Parallel-Group Study Comparing Tazarotene Cream 0.05% to TAZORAC® (tazarotene) Cream 0.05% and Both Active Treatments to a Vehicle Control in the Treatment of Stable Plaque Psoriasis

## 14.5 APPENDIX E: Amendments to the Protocol

Amendment	Date
1	12/20/2016

The following revisions were made to the protocol dated 07/26/2016.

- Updated approximate number of sites to be used.
- Section 10.4.5 Black backing on label removed
- Section 10.7.1 Updated reference in Adverse drug reaction section.
- Section 10.7.6 Pregnancy reporting start date clarified; Removed language regarding males impregnating females.

Amendment	Date	
2	12/22/2016	
Section 11.6 Updated Cochran-Mantel-Haenszel exact test in Superiority to Placebo Analysis

## **Revision History**

Tazarotene Cream 0.05%

Protocol /

0453-01-01/

## List of Abbreviations and Definition of Terms

ADaM	Analysis Data Model
AE	Adverse Event
ANOVA	Analysis of Variance
BSA	Body Surface Area
С	Celsius
CDISC	Clinical Data Interchange Standards Consortium
CI	Confidence Interval
CRF	Case Report Form
CRO	Contract Research Organization
eCRF	Electronic Case Report Form
EOS	End of Study
ET	Early Termination
F	Fahrenheit
FDA	Food and Drug Administration
Hg	Mercury
ICF	Informed Consent Form
ICH	International Conference on Harmonisation
IGA	Investigator Global Assessment
IP	Investigational Product
LOCF	Last Observation Carried Forward
MedDRA	Medical Dictionary for Regulatory Activities
mITT	modified Intent-to-Treat Population
OGD	Office of Generic Drugs
PASI	Psoriasis Area Severity Index
PD	Protocol Deviation
РР	Per-Protocol
RLD	Reference Listed Drug
SAE	Serious Adverse Event
SAP	Statistical Analysis Plan
SAS	Statistical Analysis System
SD	Standard Deviation
SDTM	Study Data Tabulation Model
	,

Tazarotene Cream 0.05%

Protocol /

0453-01-01/

#### Tazarotene Cream 0.05%

Protocol /

0453-01-01/

#### **1. INTRODUCTION**

This Statistical Analysis Plan (SAP) is based on the final Clinical Study Protocol 0453-01-01 Rev. 2 dated 12/22/2016. The SAP provides details on the planned statistical methodology for the analysis of the study data. The SAP also outlines the statistical programming specifications for the tables, listings and figures.

This SAP describes the study endpoints, derived variables, anticipated data transformations and manipulations, and other details of the analyses not provided in the study protocol. This SAP therefore outlines in detail all other aspects pertaining to the planned analyses and presentations for this study.

The following documents were reviewed in preparation of this SAP:

- Final Clinical Study Protocol 0453-01-01 Rev. 2 dated 12/22/2016
- Final eCRF Version 1.0 for

The reader of this SAP is encouraged to also read the clinical protocol for details on the conduct of this study, and the operational aspects of clinical assessments and timing for completing a subject in this study.

#### 2. OBJECTIVES

The objectives of this study are to:

- 1. Evaluate the therapeutic equivalence of the Test product, Tazarotene Cream 0.05% (Fougera Pharmaceuticals Inc.) to the Reference product, TAZORAC® (tazarotene) Cream 0.05% (Allergan, Inc.) in the treatment of stable plaque psoriasis.
- 2. Demonstrate the superiority of the efficacy of the Test and Reference (active) products over that of the Placebo in the treatment of stable plaque psoriasis.
- 3. Compare the safety of the Test, Reference and Placebo products in the treatment of stable plaque psoriasis.

#### **3. OVERALL STUDY DESIGN**

This multi-center, double-blind, randomized, vehicle-controlled, parallel-group, bioequivalence clinical study has been designed to evaluate the efficacy and safety of a

#### Tazarotene Cream 0.05%

Protocol /

0453-01-01/

generic tazarotene cream 0.05% (Fougera Pharmaceuticals Inc.) compared to the FDA Reference Listed Drug (RLD) TAZORAC® (tazarotene) Cream 0.05% (Allergan) in subjects with a clinical diagnosis of stable plaque psoriasis of at least moderate severity. Additionally, both the Test product and Reference (i.e., the RLD) products will be tested for superiority to a Placebo. Subjects with confirmed stable plaque psoriasis will apply the investigational product (IP) once daily, in the evening, to psoriatic lesions for  $84 \pm 4$  days (12 weeks).

Before any study-specific procedures are performed, all subjects will read and sign the IRB-approved ICF.

Each site will develop an individualized recruitment plan to collectively enroll approximately 855 eligible subjects, 18 years of age and older, with a clinical diagnosis of stable plaque psoriasis and meeting the inclusion/exclusion criteria. Subjects will be randomized to one of the three IPs as follows:

- Test: Tazarotene Cream, 0.05% (Fougera Pharmaceuticals Inc.)
- Reference: TAZORAC® (tazarotene) Cream, 0.05% (Allergan, Inc.)
- Placebo: Placebo (vehicle) Cream (Fougera Pharmaceuticals Inc.)

Subjects will attend the following scheduled clinic visits:

- Visit 1 Screening/Baseline: Day -14 to Day 1
- Visit 2 Interim Visit: Day  $28 \pm 4$  days
- Visit 3 Interim Visit: Day  $56 \pm 4$  days
- Visit 4 End of Study: Day  $85 \pm 4$  days

Subjects may attend unscheduled clinic visits:

• Visit 9999 – Unscheduled visit

At Visit 1, eligible subjects will be randomized to the Test, Reference or Placebo product in a 1:1:1 ratio using the system, which is an interactive response technology (IRT) system provided by the IRT provider. Study subjects will be provided with of may be dispensed to the subject at the discretion of the Investigator if the IP. subject has a high BSA affected with plaque psoriasis at the time of dispensation that would warrant additional product. At Visit 2 and Visit 3, subjects who continue to be eligible for continuation in the study can be dispensed an additional of IP, as needed based on the subject's current BSA affected and the amount of IP remaining from the tube(s) previously dispensed. Further, any empty tubes will be collected at these visits. At Visit 4, all tubes will be collected (used and unused). A subject may return for an Unscheduled Visit at any time, should they require a resupply of IP (i.e., tube lost; all IP used between visits). It is estimated that approximately , but up to may be needed to dose a subject with

Tazarotene Cream 0.05%Pi	rotocol /	0453-01-01/
--------------------------	-----------	-------------

high BSA involvement ( $\sim 20\%$  BSA) for the treatment period (depending upon their treatment response over the 12 weeks). Subjects with less BSA involvement will need significantly less IP (approximately 2 to 4 tubes).

The day that the subject administers their first dose of IP will be considered Day 1.

For all other

The subject will be instructed to apply enough cream  $(2 \text{ mg/cm}^2)$  to cover only the psoriatic lesions with a thin film  $(2 \text{ mg/cm}^2)$  once daily, in the evening, until the evening before Visit 4 (Day  $85 \pm 4$  days). There will be no application of the product on the day of the End of Study visit.

Efficacy evaluations will be based on dermatological assessments in the clinic. The primary statistical analysis of interest is the (1) proportion of subjects with treatment success (defined as none, minimal or mild disease, a score of 0, 1 or 2, within the treatment area) on the Investigator's Global Assessment (IGA) at the Week 12 visit. The secondary analyses are (1) proportion of subjects with disease severity at the Week 12 visit consistent with none or minimal, a score of 0 or 1, within the treatment area on the IGA, and (2) proportion of subjects with target site plaque elevation, scaling, and erythema scores of less than or equal to one on the PASI at the Week 12 visit. PASI is the sum of the three individual component scores.

## **Tazarotene Cream 0.05%**

Protocol /

#### **Study Schematic**

PROCEDURE	VISIT 1 (Day -14 to 1) Screening/ Baseline	VISIT 2 (Day 28 ± 4 Days) Interim Visit	VISIT 3 (Day 56 ± 4 Days) Interim Visit	VISIT 4 (Day 85 ± 4 Days)* End of Study/ Early Termination
Informed Consent	$\mathbf{X}^{\ddagger}$			
Medical History/ Demographics	X‡			
Pregnancy Test †	$\mathbf{X}^{\ddagger}$	Х	Х	Х
Vital Signs	X‡			Х
Dermatologic Assessment	$\mathbf{X}^{\ddagger}$			
IGA	X‡	X	Х	X
PASI Assessment	X‡	Х	Х	X
Application Site Reactions	Х	Х	Х	X
Inclusion/Exclusion Criteria Review	X‡			
Concomitant Medication	$\mathbf{X}^{\ddagger}$	Х	Х	X
Randomization	Х			
Dispense IP	Х	X**	X**	
Return of IP		X**	X**	X
Dispense Subject Diary/Supplies	Х	Х	Х	
Collect/Review Subject Diary		Х	Х	X
Adverse Events		Х	Х	X
Discharge from Study				Х

\* Dosing regimen is once daily in the evening for 84 days (Day 1 to Day 84) through the evening before Visit 4 (Day 85 ± 4)
 \*\* If applicable, based on use of previously dispensed product.
 \* For females of childbearing potential

‡ Procedures performed as part of the screening assessment, before randomization

Tazarotene Cream 0.05%

Protocol /

0453-01-01/

#### 4. RANDOMIZATION AND BLINDING

The IP will be randomized, packaged and blinded by an . The randomization code will be generated using a validated computer program. Each site will receive multiple, full blocks of IP in each delivery. The quantity received may vary. Randomization will be pre-planned according to a computer-generated randomization scheme. The randomization code will be retained within the which is maintained by will also retain the kit boxes numbers supplied to each site and the function of the state of the s

kit boxes numbers that have been selected for retention and are therefore unavailable for dispensing to subjects.

Upon confirmation of subject eligibility, the subject's information (i.e., subject's initials, date of , and the system will assign a birth, etc.) will be entered into randomization will then assign the number to the subject based upon subject a kit box number in a blinded fashion at Visit 1. This kit box number will correspond to a specific treatment group within ; however the treatment group will be unknown to the Investigator, the CRO, the sponsor and the subject. The site will record the randomization number and the kit box number in the subject's source documentation and drug will then dispense dispensing log. The from the kit box. The will record the tube number of the dispensed to the subject in the subject's source documentation and drug dispensing log. At Visits 2, 3 and/or Unscheduled Visit, additional IP may be dispensed to the subject, as needed. The will select an additional unused tube from the subject's previously assigned kit box, dispense it to the subject and record the tube number.

maintain the same treatment assignment throughout the study.

## 6. ANALYSIS POPULATION

#### **Per-Protocol Population**

The PP population will include subjects that comply with the protocol as follows:

- All randomized subjects who meet all inclusion and exclusion criteria.
- Make the final study visit (Visit 4) within the protocol window of Day  $85 \pm 4$  days with no PDs that would affect the integrity of the data.
- Comply with study restrictions including concomitant medications.
- Apply the IP appropriately and are within 12 weeks (Day 85 ± 4) of treatment.

Tazarotene Cream 0.05%Protocol /0453-01-01/	

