#### **10.3.3 Restrictions During the Study**

The following concomitant medications, products or procedures will not be allowed while enrolled in the study.

- Use of the following topical products on or near the treatment area:
  - Moisturizers
  - New brands of Make-up
  - o Creams, ointments, lotions, powders
  - Topical Corticosteroids
- Topical or systemic anti-psoriatic treatments (e.g., anthralin, coal tar, tazarotene, retinoids, tacalcitol, inflixamab, adalumumab, alefacept, PUVA therapy, UVB therapy, salicylic acid, calcipotriene)
- Systemic corticosteroids or systemic steroids, systemic anti-inflammatory agents or immunosuppressive drugs.

A Multi-Center, Double-Blind, Randomized, Vehicle-Controlled, Parallel-Group Study Comparing Tazarotene Cream 0.05% to TAZORAC® (tazarotene) Cream 0.05% and Both Active Treatments to a Vehicle Control in the Treatment of Stable Plaque Psoriasis

- Photosensitizers (e.g., thiazides, tetracyclines, fluoroquinolones, phenothiazines, sulfonamides)
- More than 10,000 IU/day of Vitamin A supplements
- Initiation or changes to non-antipsoriatic concomitant medication that could affect psoriasis (e.g., beta blockers, lithium) during the study
- The use of tanning booths, sun lamps, non-prescription ultraviolet light sources or excessive sun exposure
- Phototherapy
- Application of IP to unaffected skin

The treated areas should not be bandaged, covered or wrapped as to be occlusive. The use of hormonal contraceptives should not be initiated, changed or stopped during the study. Subjects should be instructed to minimize exposure to natural sunlight and to use study provided sunscreens of at least SPF 15 and wear protective clothing during the day. Subjects should not allow the IP to come in contact with the eyes, eyelids or mouth, should not use IP on skin that has eczema, and to always wash hands thoroughly after application of IP.

Subjects will be questioned about all prescription and over-the-counter (OTC) concomitant medication use (including vitamins or nutritional supplements) at each study visit. All concomitant medications will be recorded in the subject's source documents. Any subject who has violated any of the listed restrictions may be discontinued from the study. If discontinued, all End of Study/Early Termination procedures (Visit 4 procedures) should be performed.

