# **10.3.5 Early Termination**

If a subject terminates from the study early, all efforts will be made to complete Visit 4 study procedures, obtain any outstanding data and collect all IP. For early termination, the Investigator shall fully document the reason for early termination and the date of removal.

In the event that a subject discontinues from the study at any time due to an AE, the reason for discontinuation, the nature of the event and its clinical course must be fully documented. For such a subject, the Investigator should follow the subject until the AE has resolved, has become clinically insignificant, is stabilized, is confirmed to be ongoing at the end of the study, or the subject is lost to follow-up. Should a serious adverse event (SAE) be noted, procedures stated in section 10.7.4 must be followed. Should pregnancy be noted, procedures stated in section 10.7.6 must be followed.

Subjects who discontinue early because of lack of treatment effect after completing four weeks of treatment will be included in the per-protocol (PP) population as treatment failures provided they had no significant protocol deviations (PDs). Any PD that would compromise the integrity of the data will be considered significant.

Subjects who discontinue early due to worsening condition and require alternate or supplemental therapy for the treatment of their plaque psoriasis during the study should be discontinued, included in the PP population analysis as treatment failures (provided they had no significant PDs during their time of study participation), and referred for effective treatment outside of the study.

Subjects who discontinue early for reasons besides lack of treatment effect or worsening of condition should be excluded from the PP population, but included in the modified Intent-to-Treat

A Multi-Center, Double-Blind, Randomized, Vehicle-Controlled, Parallel-Group Study Comparing Tazarotene Cream 0.05% to TAZORAC® (tazarotene) Cream 0.05% and Both Active Treatments to a Vehicle Control in the Treatment of Stable Plaque Psoriasis

(mITT) population using the last observation carried forward (LOCF), provided they administered at least one dose of randomized IP and completed at least one post-dose evaluation.

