## **10.6.6 Concomitant Medication**

At Visit 1, subjects will be questioned about current and prior concomitant medication use over the 6 months before the Baseline visit. Subjects will also be questioned about ongoing or new concomitant medication use during the treatment period at Visits 2, 3 and 4. The medications to be recorded will include prescription and OTC medications and dietary supplements.

At Visits 2 and 3, any subject who has used medications restricted by the protocol may be discontinued from the study. If discontinued, all Early Termination procedures (Visit 4 procedures) should be performed.

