# STATISTICAL ANALYSIS PLAN Tazarotene Cream 0.05% Protocol / 0453-01-01/

data. Subjects with missing data will be excluded only from analyses for which data are not available, including denominators.

Subjects who discontinue early for reasons besides lack of treatment effect or worsening of condition should be excluded from the PP population, but included in the modified Intent-to-Treat (mITT) population using the last observation carried forward (LOCF), provided they administered at least one dose of randomized IP and completed at least one post-dose evaluation.

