# L16.2.3.1 Subjects Excluded from the Per-Protocol Population Data Set

Treatment Group	Subject Number	Exclusion Reason
Test	xx - xxxx	Subject did not meet IE criterion.
	XX - XXXX	Subject took prohibited medications

Reference

Placebo

Test: Tazarotene Cream 0.05% (Fougera Pharmaceuticals Inc.)
Reference: TAZORAC ® (tazarotene) Cream, 0.05% (Allergan, Inc.)
Placebo: Placebo (vehicle) Cream (Fougera Pharmaceuticals Inc.)

Path: L:\Studies\_Sas\_Codes\Clinical Trial

Created on: ddmmmyy hh:mm

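### A subject who turns to other psoriasis treatment because the cream failed can drop out of the per-protocol set that decides equivalence, instead of counting as a failure

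*SAP*

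**What the plan says.** Equivalence is declared on the primary endpoint in the PP population alone; the modified intent-to-treat (mITT) result is supportive (SAP 8.2, Protocol 11.6).

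The third PP criterion in SAP 6, worded identically in Protocol 11.3.1, requires that subjects "Comply with study restrictions including concomitant medications". Protocol 10.3.3 lists "Topical or systemic anti-psoriatic treatments" among the restrictions. In the SAP shells, T16.1.9.3.1 gives restricted medication as a PP exclusion reason and listing L16.2.3.1 gives "Subject took prohibited medications".

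Discontinuation after a breach is worded as discretionary. Protocol 10.3.3: "Any subject who has violated any of the listed restrictions may be discontinued from the study". Protocol 10.6.6, for Visits 2 and 3: "any subject who has used medications restricted by the protocol may be discontinued from the study".

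Protocol 10.3.5 deals with failure directly. Subjects who worsen and require alternate or supplemental psoriasis therapy should be discontinued and "included in the PP population analysis as treatment failures (provided they had no significant PDs during their time of study participation". Those who stop for lack of effect after four weeks of treatment are also PP failures, under the same proviso. The proviso is defined only as follows: "Any PD that would compromise the integrity of the data will be considered significant".

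SAP 8.5 gives the complementary exclusion: "Subjects who discontinue early for reasons besides lack of treatment effect or worsening of condition should be excluded from the PP population". Retention of the other two groups as failures is implied there, not stated.

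**The concern.** Taking another psoriasis treatment because the study cream is not working is a consequence of the outcome. If that act removes the subject from PP, the decisive Test-Reference comparison loses failures selectively. If failures on a weaker Test product self-treat more often than failures on Reference, deletion narrows the observed gap and can hide inferiority. If the products are truly equal but self-treatment differs between arms, deletion opens an artificial gap and costs power.

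Protocol 10.3.5 already treats need for other therapy as failure. The problem is that this principle does not clearly reach everyone to whom it should apply.

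**Working it through.** **The text, case by case.** In each case the subject worsens or does not respond, and has no other deviation.

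1. Withdrawn before taking other treatment: 10.3.5 applies, and the subject is a PP failure.
2. Takes other psoriasis treatment and is then withdrawn: 10.3.5 applies only if the use is not a significant deviation. The documents do not settle this, so the subject is either a PP failure or excluded.
3. Takes other psoriasis treatment, is kept on study and attends Visit 4 in window: 10.3.5 covers early discontinuation only, so the third PP criterion governs and the subject is deleted.

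**What can be checked.** The only visible sample-size figure is 855 randomized 1:1:1, or 855/3 = 285 per arm. Success rates, PP size and power are redacted, so the plan's calculation cannot be reproduced. What follows rests on assumptions.

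**Interval (SAP 8.2, read with the usual standard error).**
se = √[P_T(1−P_T)/n_T + P_R(1−P_R)/n_R]; limits = (P_T − P_R) ± [1.645·se + (1/n_T + 1/n_R)/2]; equivalence if both limits lie within ±0.20.

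**One data set.** Assume 200 per arm, with 80 Reference successes (40%) and 56 Test successes (28%).
- Failures kept: difference −12.0 points; se = √(0.28·0.72/200 + 0.40·0.60/200) = 0.0470; half-width 1.645·0.0470 + 0.005 = 0.0823; interval −20.2 to −3.8. Equivalence not met.
- Delete 10 Test failures (5% of subjects) and 4 Reference failures (2%): 56/190 = 29.5%, 80/196 = 40.8%; difference −11.3; se 0.0482; half-width 0.0793 + 0.0052 = 0.0845; interval −19.8 to −2.9. Equivalence met.
- The verdict can also turn the other way. With 220 per arm, Reference 40% and Test 11.8 points lower, the lower limit is −19.6. Deleting 5% of subjects, all failures, from both arms moves it to −20.6.

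**Long-run error.** Assume 200 per arm before deletion, Test exactly 20 points below Reference, and every deleted subject a true failure. Deleting a fraction r of failures gives a PP success rate of p / [1 − (1−p)r] and an arm size of 200·[1 − (1−p)r]. Example, Reference 50% and Test 30%, with r = 10% and 20%: Reference 0.50/0.95 = 52.6% (n = 190), Test 0.30/0.86 = 34.9% (n = 172), difference −17.7 points. The probability of declaring equivalence, by full binomial enumeration, is:

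| Deleted (Reference v Test) | 50/30 | 60/40 | 70/50 |
|---|---|---|---|
| None | 3.9% | 3.8% | 3.9% |
| 2% v 5% of all subjects | 5.2% | 5.5% | 6.5% |
| 5% v 10% of failures | 6.3% | 6.7% | 7.5% |
| 10% v 20% of failures | 9.2% | 11.8% | 14.4% |
| 20% v 20% of failures | 2.8% | 4.3% | 6.1% |

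With both true rates at 50%, deleting 10% v 20% of failures lowers equivalence power from 97.6% to 93.6%.

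**The case against.** - **10.3.5 is the specific rule and says these subjects should be discontinued.** The permissive sentences in 10.3.3 and 10.6.6 are general and cover breaches as minor as a moisturizer. This stands in part. Followed as written, 10.3.5 sends most such subjects to withdrawal and PP failure, so case 3 needs a site to keep the subject on study despite 10.3.5. The permissive wording leaves room for that, and once it happens no visible rule scores the subject.
- **10.3.5 must override the general PP list.** An early withdrawal cannot meet the Visit 4 window criterion either, so on this view 10.3.5 can override the medication criterion too. That is a reasonable reading of case 2, but the proviso on significant deviations leaves it open. It does not reach case 3.
- **The PP lists are partly blacked out and the shells are illustrative.** Both are true; SAP 9 says the shells may not reflect every aspect of the study. A failure rule could sit in hidden text. The point therefore rests on the unqualified visible criterion and on 10.3.5, not on a missing sentence.
- **There are safeguards.** Equivalence is also run in mITT, exclusions are tabulated by reason and arm, and the parties conducting the study are blinded until database lock. These help a reader detect the problem, but PP alone decides.
- **Excluding users of prohibited medication is normal in a PP analysis.** Agreed for use unrelated to the outcome. It does not answer the case where the use follows from treatment failure.

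**Conclusion.** The gap is real but narrow. The visible text leaves two routes, cases 2 and 3, by which a treatment failure can leave the deciding population because of its outcome.

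A reader might infer that the SAP contradicts the protocol. It does not: the criterion is the same in both documents, and the tension lies inside the protocol. A reader might also infer that every failure who needs other treatment is lost. The documents do not support that, because 10.3.5 calls for discontinuation and PP failure.

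A larger error can be computed: deleting 15% of Reference and 30% of Test failures gives 15-26%. In the 50/30 case that means 15 Reference and 42 Test subjects self-treating and being removed. Nothing in the documents supports such counts, or a twofold difference between two 0.05% creams of the same drug.

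Under the assumptions above, modest unequal use (2% v 5% of subjects) raises false equivalence from 3.8-3.9% to about 5-6.5%. Deleting 5% v 10% of failures gives 6-8%, and 10% v 20% gives 9-14%. With equal fractions it stays at about 3-6% and can move either way. In a single data set the verdict changes only when a limit is already near the margin. The inconsistency is clear; its effect depends on unequal use between arms, which is unknown.

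**What to change.** Add to the third PP criterion in SAP 6 and Protocol 11.3.1, as an analysis rule only:

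*A subject who, after the first dose, started a topical or systemic anti-psoriatic treatment, a topical or systemic corticosteroid, an immunosuppressive drug or phototherapy listed in 10.3.3, for worsening or lack of effect of the study psoriasis, and who has no other significant PD, stays in PP and is scored a treatment failure on the primary and both secondary endpoints, whether or not discontinued. This use alone is not a significant PD under 10.3.5. All other prohibited use remains under the existing exclusion. Cases are classified blind, before database lock.*

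The limit to these classes matters. 10.3.3 also bans moisturizers and ordinary creams near the treatment area, and a rule covering every prohibited product used for psoriasis would fail a clear subject who once applied a moisturizer. If blacked-out text already contains such a rule, confirming that it covers cases 2 and 3 is enough.

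Cost: a short SAP addition, a matching protocol amendment with IRB review (Protocol 12.3.3), and a blinded review of medication records; listing L16.2.4.3 already carries indication and dates. PP success rates would fall slightly, and PP would hold a few subjects with a medication deviation. Who is withdrawn or treated does not change.
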